3.0 Intervention to be studied

ARMS 1, 2, and 3. Design Overview. Design Overview and Project Timeline:

This 12-week feasibility trial will use a 3x3 repeated measures (treatment x time) between groups randomized trial design to compare Otago (OG) vs. Otago + Yoga (GYB) vs. Otago + GYB + Behavioral Activation (ie., the complete *Activate for Life* intervention) in low-income older adults with chronic pain and/or fatigue at baseline, post-treatment and 3- month follow-up. Participants will be randomly assigned to one of the three conditions. Daily self-monitoring of program component adherence, PROMIS self-report measures of pain, fatigue, anxiety, depression, and social support. Physical activity measures will include actigraphy, steps per day, 2-minute timed walk test, sit-to-stand test, and Mini-Best. Participants will be 30 adults (10 per group) age 60 and above with a PROMIS pain interference score of eight or above and/or a PROMIS pain behavior score of 15 or above (cut points based on a T-score that rescales the raw score into a standardized score with a mean of 50 and a standard deviation (SD) of 10 for each of these instruments).

Alternative design: The progressive nature of this feasibility trial allows the proven evidence-based modalities of OEP and GYB to be combined with behavioral activation to not only address physical activity but also the mental health aspects of chronic pain and fatigue. Therefore, this feasibility trial scaffolds the components to show that the modalities of OEP and GYB are effective and their success is dependent on motivation. However, we are not testing these three interventions alone, or in every possible combination.

Supplemental ARM 4 - Design Overview:

For the supplement, the CON SSMC will leverage its expertise in technology-enhanced SM interventions and community-engaged research to establish the feasibility of an mHealth GYB (physical activity + breathing) intervention on adherence, acceptability, and short-term health outcomes related to burden in CG of PWD. We will recruit 20 older CG who are caring for PWAD/ADRD receiving services in social and medical RCCs connected with an active R01 investigation, Mealtime Partnerships for People with Dementia at Respite Centers and at Home (R01 NR016466; PI: [name]). Two data collection points will occur at the beginning (Week 1, pre-intervention, or baseline, "V1") and end (Week 12, post-intervention; "V2") of the 12-week study. Preliminary changes in CG health indicators such as physical function, fatigue, depression, and social isolation as well as CG/PWD QoL will be examined to support a future RCT and build opportunities for faculty training in dyadic analyses. The relationship between salivary stress biomarkers (cortisol and 1,5-anhydroglucitol, or 1,5- AG) and self-reported reduction in stress symptoms will also be examined. Based on results from past SSMC studies, we posit that adherence will be adequate ($\geq 80\%$ scheduled activity compliance), satisfaction will be high ($\geq 80\%$), attrition will be limited ($\leq 25\%$), and follow-up data collection sufficient ($\leq 20\%$ missing data) to establish the validity of a future, full-scale RCT.

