AIM 1. Integrate evidence-based components of “*Activate for Life*” a telehealth delivered, nurse-led behavioral health program for low income older adults targeting pain and fatigue through balance training (Otago), strengthening and mindfulness (Yoga), and affective state (Behavioral Activation).

We hypothesize that the evidence-based Otago and Yoga components of this intervention will integrate with the ‘infrastructure’ format of the Behavioral Activation mental health treatment insofar as a 60-minute session, 6-10 session intervention will be developed.

Aim 2. Test the feasibility of Activate for Life in terms of its individual components by comparing Otago vs. Otago+Yoga vs. Otago+Yoga+Behavioral Activation in a pilot RCT design with 10 participants in each of the 3 conditions in terms of recruitment, intervention ‘dosage’ (frequency/density), adherence, treatment satisfaction, attrition, rates of missing data, and other feasibility metrics, including qualitative feedback from participants for final intervention refinement.

We hypothesize that adherence will be adequate (65% scheduled activity compliance), satisfaction will be high (above 80%), attrition will be limited (below 25%), and followup data collected (below 20% missing data)

AIM 3. Determine an initial efficacy signal for the intervention that will inform future power estimates.

We hypothesize that the combined intervention will show significant within subject improvement over baseline on measures of pain, fatigue, and depression.

Supplemental ARM 4 - AIM 4. Test the feasibility of a 12-week e/mHealth gentle yoga+yogic breathing (GYYB) intervention for alleviating symptoms of burden in aging Caregivers (CG) of persons (N=20) with dementia (PWD); measure initial changes in stress and QoL indicators in CG and PWD (post- vs. pre-intervention).

Impact. This pilot feasibility study will set the stage for a full scale RCT demonstrating the additive benefit (if present) of each additional component over the CDC approved balance intervention Otago. Self-management of pain and fatigue through strength and balance training in low-income older adults can improve quality of life, decrease health care costs, and increase the ability of the person with these symptoms to age in place.

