10.0 Study Design / Methods

ARMS 1, 2, and 3: Once a participant has consented and been enrolled they will be randomized by computer (stratified by gender) to one of three treatment groups and the PI and/or their designee will set up a home visit appointment to meet with the participant to obtain baseline data (Table 1). Part of the baseline screening includes the PROMIS Emotional Distress-Depression Short Form 8a. If a participant scores in the severe depression category (raw score 33 and above) a referral will be placed to a mental health professional. Additionally, participants that score in the moderate depression category (raw score 23 to 32) further screening for suicidal ideation will take place. If the participant would admit to suicidal ideation at any time during the study, an emergent mental health consult will be placed through the Charleston/Dorchester Mental Health Center Assessment/Mobile Crisis.

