Fatigue Lower extremity strength Balance and Function Walking capacity	30 Second Chair Stand Test (not determined) ⁴² Mini Balance Evaluation Systems Test (MiniBEST) (0.91) ⁴³ Two Minute Walk Test (0.82) ⁴⁴	Baseline; Study end Baseline; Study end Baseline; Study end
Self-report measures Function Depression Social support Self-efficacy	PROMIS Physical Function (0.95) ⁴⁵ PROMIS Depression Short Form 8a (0.95) ⁴⁶ Revised UCLA Loneliness Scale (0.94) ⁴⁷ Pain Self-Efficacy Scale (0.93) ⁴⁸	Baseline; Study end Baseline; Study end Baseline; Study end Baseline; Study end
Adoption Adherence	Participation in weekly self-management telehealth visits; frequency of participation in Otago and/or Yoga as recorded in participant diary and data from activity tracker; frequency of use of self-management techniques as recorded in participant diary; # of patients who successfully complete self-management program; # of and reasons for dropouts	Tracking forms; weekly review of participant diary; weekly assessment of feedback; end of study participant interviews and satisfaction questionnaires
Acceptability		

Endorsement	Usability of tablet technology and activity tracker; # and types of problems encountered; participant satisfaction with self-management program and technology	Assess at weekly team meetings; acceptability checklist and tracking forms; end of study participant interviews and satisfaction questionnaires
Implementation		
Technology	# of problems encountered with tablet, activity tracker, vital sign equipment; # and types of problems encountered with study setup; was fidelity to training protocol maintained; was orientation completed as planned; was standardized checklist used to instruct participants; assessment of participant for suggestions; # of changes made to intervention based on suggestions	Tracking forms; weekly team meetings; end of study participant interviews and satisfaction questionnaires
Site set up		
Consistency of intervention		
Maintenance		
Projection of future adoption	# patients who would continue intervention; potential for future applications	End of study participant interviews and satisfaction questionnaires

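### The design cannot show that Otago is effective or that success depends on motivation, and it can estimate yoga only as an add-on to Otago

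*Protocol*

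**What the plan says.** Protocol section 3.0 sets out a randomised trial to "compare Otago (OG) vs. Otago + Yoga (GYB) vs. Otago + GYB + Behavioral Activation". Section 10.0 confirms that participants are allocated at random: "they will be randomized by computer (stratified by gender) to one of three treatment groups". Aim 2 in section 1.0 gives the size as a "pilot RCT design with 10 participants in each of the 3 conditions".

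Under the label Alternative design, section 3.0 then says the components are scaffolded "to show that the modalities of OEP and GYB are effective and their success is dependent on motivation". The following sentence qualifies this: "we are not testing these three interventions alone, or in every possible combination".

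Elsewhere the ambition is smaller. Aim 2 compares the arms on feasibility measures. Aim 3 looks for an initial efficacy signal to inform later power calculations, and its hypothesis is within-subject improvement in the combined arm. The Impact paragraph leaves the additive question to a later full-scale trial.

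Table 2 in section 10.0 lists measures of pain, fatigue, strength, balance, walking, function, depression, loneliness, pain self-efficacy, adherence and acceptability. It lists no motivation instrument. The SAP plans a repeated measures ANOVA across the three arms at 0.05. It names no pairwise contrasts, plans confidence intervals only for feasibility measures, and has no mediation or moderation analysis.

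**The concern.** The sentence promises two conclusions that the design cannot deliver: that Otago is effective, and that success depends on motivation. A third, that GYB is effective, can be addressed only in a narrower form.

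This matters because Aim 3 is framed as within-subject improvement. Participants enter on PROMIS pain interference or pain behavior scores (section 5.0), and both scales are outcomes in Table 2. Some improvement at study end is therefore expected from regression to the mean alone, and every arm also has weekly telehealth contact. Read alongside the section 3.0 sentence, an uncontrolled improvement could be taken as evidence that the components work. The same reading could pass into the planning of the larger trial, which needs estimated increments rather than pre-post changes.

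**Working it through.** The protocol gives no power-based figure to reproduce. Its sample size rests on recruitment and on avoiding contamination between sites; the only arithmetic is 3 × 10 = 30, which agrees.

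**Step 1: what the arms identify.** Write T for change that would occur without any component (time, attention, regression to the mean). Write O for Otago, Y for adding GYB to Otago, and B for adding the Behavioral Activation package to Otago+GYB. Expected change by arm:

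- Arm 1: T + O
- Arm 2: T + O + Y
- Arm 3: T + O + Y + B

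Arm 2 − Arm 1 = Y, and Arm 3 − Arm 2 = B. O always appears together with T, so no combination of the three arms separates them. Y is the effect of GYB given Otago; GYB without Otago is not observed in these arms. Supplemental Arm 4 gives yoga alone, but to caregivers, in one arm with no comparator, so it does not fill the gap.

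**Step 2: motivation.** Dependence on motivation needs either a measured motivation variable with a planned analysis, or a contrast that varies motivation alone. Neither exists.

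- In Table 2 the nearest items are pain self-efficacy, a different construct, and adherence, which is behaviour.
- B is a package: section 10.0 says Behavioral Activation addresses affect as well as motivation, and it brings its own sessions.
- Section 2.0 lists a triggered nurse session on motivation and problem solving as a feature of the whole project, so motivational support is not confined to Arm 3.

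**Step 3: precision of the identified increments.** The documents give no SD, so results are in SD units, two-sided 0.05 (sidedness is not stated in the SAP; two-sided is assumed), for one comparison at one time point.

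Unadjusted half-width = t(0.975, 2n−2) × √(2/n):

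- n = 10: 2.101 × 0.447 = 0.94 SD
- n = 8: 2.145 × 0.500 = 1.07 SD
- n = 7: 2.179 × 0.535 = 1.16 SD

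The values 8 and 7 reflect Aim 2's expectation of attrition below 25%: 25% of 30 is 7.5, so at most 7 dropouts and 23 completers, or 7 to 8 per arm. These figures count completers only; the SAP's mean substitution adds no information.

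With baseline adjustment at an assumed correlation r, half-width ≈ t(0.975, 17) × √(2/10) × √(1−r²):

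- r = 0.5: 2.110 × 0.447 × 0.866 = 0.82 SD
- r = 0.7: 2.110 × 0.447 × 0.714 = 0.67 SD

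By the noncentral t distribution, 10 per arm has about 18% power for an assumed difference of 0.5 SD and 40% for 0.8 SD, unadjusted. The difference detectable with 80% power is about 1.32 SD.

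**The case against.** The strongest reply is that this is one loose sentence of rationale, qualified by its neighbour, and that it drives no aim or analysis. The aims are feasibility and an early signal, and the SAP sets no effectiveness criterion for Otago and no motivation test. Much of this stands and limits the seriousness of the point: the trial's feasibility purpose is untouched. But the neighbouring sentence contradicts the claim without withdrawing it, and says nothing about motivation.

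Several stronger readings are tempting and are not supported:

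- **That the nested arms can show nothing about GYB.** Otago+GYB against Otago is a sound randomised add-on comparison and needs no untreated arm. Its weakness is precision, not structure.
- **That an untreated control is the only remedy for Otago.** Any concurrent comparator without Otago would serve, and a feasibility pilot need not have one if it does not make the claim.
- **That the protocol claims additive benefit for this trial.** The words "demonstrating the additive benefit (if present) of each additional component over the CDC approved balance intervention Otago" describe the later full-scale trial. They show restraint rather than overreach.
- **That contact time spoils only the Behavioral Activation contrast.** GYB adds a weekly one-hour instructor-led group session for 12 weeks (section 10.0), so both increments include extra contact. The documents give no total contact time by arm.

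The SAP is dated 03/12/2021 and written in the past tense, so new contrasts may no longer be pre-specifiable. That objection also stands and is reflected in the fix.

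**Conclusion.** The sentence in section 3.0 goes beyond the design. Otago's effectiveness and dependence on motivation cannot follow from any result of this trial; that conclusion rests on the arm structure, the measures listed and the planned analysis, not on any numerical assumption. GYB is estimable only as an increment over Otago, and Behavioral Activation only as a whole package added to Otago+GYB, each including its extra contact.

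The size figures describe how imprecise those two increments are and do not bear on identifiability. Across the cases worked, the half-width runs from 0.67 to 1.16 SD. The low end depends on 10 completers per arm and an assumed baseline correlation of 0.7; the high end is unadjusted with 7 completers. The documents supply neither an SD nor a correlation.

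This is a defect in what the trial says it will conclude and in how the SAP reports the efficacy signal. It does not invalidate the trial.

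**What to change.** 1. In Protocol section 3.0, replace the sentence with: *The trial assesses feasibility and estimates, with 95% confidence intervals, the increment from adding GYB to Otago and the increment from adding the Behavioral Activation package, including its extra contact, to Otago+GYB. It does not test the effectiveness of Otago or GYB alone, or motivation as a mechanism.*
2. In the SAP, report these two contrasts with 95% intervals alongside the repeated measures ANOVA. If the analysis has already been done, label them post hoc. The three-arm test alone does not give the increments and their uncertainty, which Aim 3's power-planning purpose needs.
3. Wherever Aim 3's within-arm change is reported, describe it as uncontrolled.

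The cost is wording and a small amount of analysis on data already planned; no participants, visits or measures are added. The drawback is a less favourable stated claim, with visibly wide intervals.

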4.0 Study Endpoints (all ARMS)

Study end points include: Successful study completion, participant consent withdrawal, and PI termination due to failure to adhere to the protocol, loss of contact with the patient, and/or unexpected adverse events.

5.0 Inclusion and Exclusion Criteria/ Study Population

Inclusion criteria for ARMS 1, 2, and 3 are as follows:

- Males and females 60 years of age and older living in a Humanities Foundation apartment complex, HUD funded housing or living at 150% of poverty level
- PROMIS pain interference score of eight or above and/or a PROMIS pain behavior score of 15 or above
- Able to ambulate 150 feet with or without the use of an assistive device
- Able to follow simple instructions
- Able to read, speak, and write English,
- Able to operate tablet device and wearable activity tracker,
- Not currently enrolled in an exercise program.

Exclusion criteria for ARMS 1, 2, and 3 are:

- Inability or unwillingness of participant to give informed consent,
- Physical, cognitive, sensory or psychiatric disability that would limit participants from engaging in self-management program as noted by a Mini-Cog²⁶ score of 0-2.
- Unwillingness to wear a physical activity tracker during the course of the study.

Inclusion criteria for Supplemental ARM 4 are:

- CG must be able to speak and read English
- CG must be 45 years of age or older
- CG must be able to provide consent for themselves
- CG must live with or on same property as the PWD
- CG be primarily responsible for care provision of the PWD in the home (i.e., is not paid for services; provides 4 hours or more of care/day; assists with ADLs)

Exclusion criteria for Supplemental ARM 4 are:

- CG for whom yoga techniques would be detrimental due to physical limitations,
- CG who are enrolled in other Yoga-related clinical trials, or who are currently engaged in regular Yoga activity once per week or more.

6.0 Number of Subjects

The number of participants enrolled under ARMS 1, 2, and 3 will be 30 adults age 60 and over. Thirty participants should allow for recruitment of 10 participants from at least 3 different Humanities sites to avoid cross-contamination of study groups. The number of participants enrolled under Supplemental ARM 4 will be 20 adults aged 45 and older. The total number of participants under this research project will be 50.

7.0 Setting

ARMS 1, 2, and 3. The Humanities Foundation is a non-profit affordable housing provider in South Carolina, Georgia, Virginia, and Louisiana. The Foundation, in place for over 20 years, has 1400 units of affordable housing for low-income populations including disabled, single mothers, and senior citizens. To qualify to live in these low-income facilities the residents must have income that is no more than 60% of the Area Median Income. The study sites will be the six Humanities Foundation older adult living complexes in the Charleston, SC area, other HUD funded housing, or low-income persons living at 150% of poverty level. The study would be conducted within the facilities community meeting room and in individual participants apartments. All research activities and study procedures

will be conducted by IRB approved MUSC study personnel. No employees and/or agents of Humanities Foundation will engaged in any research activities.

Supplemental ARM 4 Setting: All CG participants will be recruited from within the greater Charleston Tri-county area. All research activities and study procedures will be conducted by IRB approved MUSC study personnel. Research activities will take place at CON as well as at participant's homes.

8.0 Recruitment Methods

ARMS 1, 2, and 3

IRB approved flyers will be distributed to the residents at each of the Humanities Foundation apartment complexes as well as posted in general public community areas. Educational sessions, headed by the PI, will also be held at the complexes to allow potential participants to learn about the program and ask pertinent questions. Individuals who are interested in the program will be directed to contact the study PI or their designee via phone or at the information sessions. If interested participants meet the eligibility criteria and voluntarily consent to join the study they will be enrolled.

Additionally, we will recruit individuals who have had recent services through MUSC ED that have authorized research contact permission in MyChart through the MUSC electronic 'opt in' EPIC designation and have been identified by the Bioinformatics Center (BMIC) as over 60 years old, have had a recent fall and reside at one of the Humanities Foundation complexes. We will then contact potentially eligible patients by telephone to determine if they are interested in participating in the study and if so, schedule an informed consent meeting.

Supplemental ARM 4:

All CGs will be recruited through local affiliations with social and medical Respite Care Centers (RCC) and home health services for families of PWD established through our Mealtime Partnerships R01 study. We will devise and use IRB approved study recruitment flyers and letters that will be disseminated electronically and handed to RCC caregivers, as well as directly contact CGs by phone that have previously expressed and noted their agreement to be contacted regarding other research studies as documented on their consent form. In addition, we will conduct outreach activities and engage outside network RCC providers in the local community to inform them of the opportunity for their clients to participate in this study.

9.0 Consent Process (ALL ARMS)

In-person

Research activities will not be conducted without the patient's written informed consent. Informed consent will be conducted by the PI and/or their designee as noted on the IRB study delegation log, and will occur in the comfort and privacy of a private room at the facility or the participant's place of residence prior to any screening procedures being conducted and/or data collection. Potential participants will be given the informed consent document to read and review in advance, and/or may have it read to them by the researchers, if they prefer. After reviewing the consent document, the patient will be given the opportunity to ask any questions about the study that they may have, and will be requested to demonstrate what is expected from them should they agree to enroll in the study through a questioning of their understanding of study procedures and risks. Prior to consenting, all questions will be resolved to the patient's satisfaction. If a participant does not appear to understand the information contained within the Consent document or of what is expected of them as a study subject, then the study coordinator will review the consent document again with the participant. If after this second review, the subject does not demonstrate an understanding, they will not be enrolled in the study. Only participants, with no observed cognitive impairment, will be consented and enrolled into the study.

The consent form will meet the requirements of the Code of Federal Regulations and the MUSC Institutional Review Board; and, include the following elements:

- The purpose, nature, and objectives, potential risks and benefits of the intended study.
- The length of study and the likely follow-up required.
- The name and a contact of the investigator(s) responsible for the protocol.
- The right of the participant to accept or refuse study interactions and to withdraw from participation at any time.

All consented subjects will be given a copy of their executed and countersigned Consent form. The researchers will maintain a means of contact with all enrolled study participants in the eventuality that reconsenting of currently enrolled participants is needed and/or the disclosure of new study information is warranted to previously enrolled participants.

E-Consent

In light of institutional guidelines pertaining to COVID-19 and the conduct of human subject research, study participants may also be consented using MUSC IRB approved REDCap e-consent process.

In the case of obtaining e-consent, potential participants will have been introduced to the opportunity to participate in the study. All potentially interested participants will be referred to the MUSC research team either directly with the participant's verbal permission or self-referred through contact information on the study recruitment flyers. Upon making contact with the referred individual, the researchers will identify themselves, indicate how they received the individual's personal contact information, provide the reason for the call and an overview of the study and study procedures. If the individual expresses an interest in learning more about the study and/or becoming a participant, the researchers will ask the individual for a working email address where the e-consent will be sent and set-up a follow-up telephone call for the e-consent process. These individuals will be allowed as much time as needed to read and review the e-consent document in the privacy of their own home or at a place of their choosing. During the e-consent call, the researcher will review the e-consent document in its entirety and be available to further answer any questions that they may have prior to the individual adding their respective signature to the form and submitting the e-consent. Upon submitting the e-consent, a REDCap trigger will immediately notify the researcher, who will then provide their countersignature to the document. All e-consents will be maintained in the REDCap study e-consent database for regulatory purposes and compliance monitoring. All participants will be electronically sent a copy of the fully executed e-consent form to their email address. Hard copies will be mailed to participants upon request.

